Follow-up time will be calculated separately for each study endpoint. Patients will be followed starting the day after initial exposure until the first of the following censoring events: (1) the study endpoint of interest, (2) death (for those who do not have the endpoint of interest), or (3) end of available data for those who do not have the event of interest (i.e., censoring due to end of available EHR data). Person-time will be calculated by summing the days from cohort entry (day 0) to the date of the first relevant censoring event.

To test the robustness of assumptions about the date of censoring, analyses with differing censoring definitions will be performed, and estimates compared:

- To assess whether the censoring date needs to be adjusted, the physician consultant will review a random sample of patient health profiles to determine whether there is a clear indicator of censoring. Insofar as there appears to be a clear indicator of censoring, the physician will record this date (blinded to exposure), and this information will be used to

adjust the censoring date. Indeed, this information may be treated as an annotation for a machine learning model.

- To account for a patient still being on the insurance plan but not accessing the healthcare system, adjust the end of follow-up to be 6 months, 1 and 2 years following their last healthcare encounter in the EHR.
- To assess the reliability of our method for computing time until censoring in the EHR, compare follow-up times in the EHR to those observed in the claims enrollment files using a subset of those with EHR and claims data.
- To test robustness of the method for computing follow-up time in the EHR, compute the distribution of follow-up times based on enrollment spans within the subset of individuals with claims and EHR data and apply the median follow-up time within populations with particular health profiles.
- To implement a more specific definition of follow-up time, assume that a last healthcare encounter with a primary care provider, endocrinologist, or geriatric care provider in combination with no death information is the end of enrollment.

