### 8.1 Study Size

According to the most recent available data from Arcadia (delivered to Exponent November 2022), ~37,000 patients had an apparent initiation of NB. Of those patients ~64% had linked, adjudicated claims data at some point in time. Seventy percent of apparent initiators were women.

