## 9.3 Crude Incidence Rate Difference (IRD) and Incidence Rate Ratio (IRR) Estimates

The incidence rate for each group is the cumulative number of observed endpoint events, divided by the total person-years of follow-up. The crude IRD is the absolute difference in the observed incidence rate between initiators of NB and initiators of lorcaserin, with no adjustment for differences in patient characteristics between groups. The crude IRR is the relative difference (i.e., ratio) in the observed incidence rate of initiators of NB, divided by the observed incidence rate for initiators of lorcaserin, with no adjustment for differences in patient characteristics between groups.

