### 9.5.3 Statistical Model for Cohort Analysis

For all primary study objectives, weighted Poisson models will be used to estimate IRDs and IRRs (and 95% CIs), adjusted for all covariates included in the PS model. Robust variance estimators will be used to account for the weighting. Analyses will be conducted amongst the overall NB cohort and also stratified by initiators of CONTRAVE® and those with overlapping, concomitant use of Naltrexone and Bupropion.

For the secondary objective of assessing the comparability of findings in a RWD cohort with the lorcaserin clinical trial, we will conduct a time-to event analysis in the propensity-score matched cohort. We will produce hazard ratios (HR) and 95% confidence intervals using a weighted Cox proportional-hazards model with the stratification factor as a covariate.

Additionally, informed by previous work in the RCT DUPLICATE Initiative, we will examine the following metrics in concert to assess the comparability in findings between the CAMELLIA-TIMI 61 trial and findings in the data:

- Regulatory agreement, which is the ability of the study using RWD to replicate the direction and magnitude of the RCT;

- Estimate agreement, defined as a HR from the replication study that was within the 95% CI for the RCT estimate;
- Standardized difference between the RCT and replication effect estimate, with a p-value < 0.05 considered statistically significant.

Conditional logistic regression models will be used to compare the odds of exposure to NB in the hazard window to the odds of exposure in the referent window (i.e., odds ratio) for the case cross-over design.

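### The group-median follow-up analysis separates person-time from the period in which events could be observed, so its result cannot be cleanly attributed to the censoring assumption

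*Combined protocol and SAP*

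**What the plan says.** Under the main rule in section 6.5.2, each patient is followed to the endpoint, death or end of available data, and "Person-time will be calculated by summing the days from cohort entry (day 0) to the date of the first relevant censoring event". Section 9.3 then defines the rate: "The incidence rate for each group is the cumulative number of observed endpoint events, divided by the total person-years of follow-up". Section 9.5.3 adds that "weighted Poisson models will be used to estimate IRDs and IRRs (and 95% CIs), adjusted for all covariates included in the PS model".

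Five robustness analyses of the censoring date follow in section 6.5.2. They share one purpose: "To test the robustness of assumptions about the date of censoring, analyses with differing censoring definitions will be performed, and estimates compared". The fourth will "compute the distribution of follow-up times based on enrollment spans within the subset of individuals with claims and EHR data" and then "apply the median follow-up time within populations with particular health profiles".

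The plan does not say:
- who receives the median (all patients, unlinked patients or event-free patients);
- whether it is pooled or arm-specific;
- whether it replaces or caps a patient's own time;
- how events before and after it are handled;
- what defines a health profile.

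The third analysis uses individual enrollment files, but only to compare lengths of follow-up. It does not state that the effect will be re-estimated.

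**The concern.** A rate needs a numerator and a denominator drawn from the same observed time. Total person-years equal the number of patients times mean follow-up. A group median equals that mean only by coincidence or symmetry.

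Once a median is assigned, some patients' EHR data end before it. They are credited with event-free time in which an event could not have been recorded. Other patients have data beyond it, and their later events must be either dropped or counted without matching time.

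The IRD and IRR from this check could therefore move, or stay still, because of the substitution and not because the end-of-EHR rule is wrong or right. Section 6.1 gives different accrual windows (NB from September 2014, lorcaserin from 2012), so unequal follow-up by arm is plausible. A median set by health profile alone would then act differently on the two arms. The same difficulty reaches the comparability study, whose "weighted Cox proportional-hazards model with the stratification factor as a covariate" needs individual times.

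**Working it through.** **The plan's own figure.** The only design figure is power above 80% for a relative risk of 2.0 (section 8.2), and it does not depend on this analysis. It is consistent with the stated inputs but cannot be reproduced exactly, because the text gives no alpha or mean follow-up. Take 37,000 v 16,000 patients, 4 v 2 per 1,000 person-years, and two-sided alpha 0.05 (assumed). One year of mean follow-up gives 148 and 32 events, SE of the log ratio = sqrt(1/148 + 1/32) = 0.195, and power = Φ(0.693/0.195 − 1.96) = 94%. At 0.5 years power is 71%; it reaches 80% at about 0.62 years.

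**Set-up.** Let C be a patient's own follow-up, m the median and λ the event rate, with rare events (2 per 1,000 person-years, section 8.2). To isolate the substitution, assume claims and EHR follow-up have the same distribution. A sound check should then return a multiplier of 1.00.

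- All events kept: rate multiplier = E[C]/m.
- Events after m dropped: rate multiplier = E[min(C, m)]/m. With rare events this also covers the reading in which endpoint and death keep their own dates and only the end-of-data date is replaced.
- Median used only as a cap, min(C, m): multiplier 1.00 under a constant hazard.

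**Same follow-up in both arms (assumed shapes, no upper limit).**

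| Shape | E[C]/m | E[min(C,m)]/m |
|---|---|---|
| Exponential | 1/ln 2 = 1.44 | 0.5/ln 2 = 0.72 |
| Lognormal, σ 0.5 | exp(0.125) = 1.13 | 1.13·Φ(−0.5) + 0.5 = 0.85 |
| Lognormal, σ 0.8 | exp(0.32) = 1.38 | 1.38·Φ(−0.8) + 0.5 = 0.79 |
| Lognormal, σ 1.0 | exp(0.5) = 1.65 | 1.65·Φ(−1) + 0.5 = 0.76 |
| Weibull, shape 0.7 | Γ(1 + 1/0.7)/(ln 2)^(1/0.7) = 2.14 | 0.68 |

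The Weibull 0.68 is Γ(1 + 1/0.7)·P(1/0.7, ln 2)/(ln 2)^(1/0.7), where P is the regularised lower incomplete gamma function.

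With follow-up capped at 7.5 years (assumed), lognormal σ 0.8 and median 1.50 years has mean 2.00. A true rate of 2.00 per 1,000 becomes 2.66 with all events kept (x1.33) or 1.58 with later events dropped (x0.79). About 41% of events fall after the median there, and about 49% for an exponential. The IRD scales with the rates. The IRR multiplier is 1.00, because both arms are scaled alike.

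**Follow-up differing by arm, pooled median (arms weighted 37:16, cap 7.5 years).** With all events kept, m cancels and the IRR multiplier is E[C, NB]/E[C, lorcaserin].

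| Assumed follow-up, NB v lorcaserin | All events kept | Later events dropped |
|---|---|---|
| Exponential, 1.5 v 2.5 y before cap | 1.49/2.38 = 0.63 | 0.69/0.79 = 0.87 |
| Exponential, 2.0 v 2.4 y before cap | 1.95/2.30 = 0.85 | 0.71/0.75 = 0.95 |
| Lognormal, median 1.5, σ 0.8 v median 2.0, σ 0.5 | 2.00/2.26 = 0.88 | 0.84 |

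The pooled medians are about 1.20, 1.46 and 1.69 years. In the first row a true IRR of 2.00 would appear as 2.00 × 0.63 = 1.26 with all events kept. Arm-specific medians give 1.02 to 1.18 with all events kept and 0.93 to 1.00 with later events dropped. The pooled multipliers fall below 1 because lorcaserin was assumed to have the longer mean follow-up; reversing that would reverse the all-events-kept direction.

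**The case against.** The strongest reply is that the bullet is introduced as a censoring definition, so only the end-of-data date should change. Endpoint and death would still stop a patient's time, and later events would be ignored as under any censoring date. This disposes of the keep-all-events branch for anyone who reads it so, but it does not rescue the analysis. Patients whose EHR data end before the median still gain time in which nothing could be recorded, which is the later-events-dropped column.

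A second reply is that the median may act as a cap. Events and time then stay linked and the multiplier is 1.00 under a constant hazard. The text does not say this, and a cap would leave the end-of-EHR assumption untested for patients whose data end before the median.

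Several stronger conclusions are tempting, and the documents do not support them:

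- A reader might infer that every patient receives the median. The plan is silent on scope.
- A reader might infer that the check cannot test anything. With the same follow-up distribution in both arms the IRR is essentially unaffected, and the cap version is a valid though limited check.
- A reader might take the exponential +44% as the size of the error. It needs both an assumed shape and the retention of events after the assigned date. Accrual in a bounded window could give nearly symmetric follow-up, where mean and median are close.
- A reader might infer from section 8.1 that enrollment dates during follow-up exist for most NB initiators. The text says "Of those patients ~64% had linked, adjudicated claims data at some point in time", which does not establish coverage at the index date or afterwards. Carrying claims information to unlinked patients is a plausible purpose of this bullet.

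It also stands that this is one of five checks, with no decision rule attached.

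**Conclusion.** The point holds on the most natural reading, in which the median stands in for patients' own end of data. Rates and the IRD are then distorted in a direction set by an unstated choice. Under the assumed skewed shapes the multiplier is 1.13 to 2.14 with all events kept. With later events dropped it is 0.72 to 0.79 in the exponential and lognormal σ 0.8 examples, and 0.68 to 0.85 across all the shapes tabulated. The IRR is safe if follow-up has the same distribution in both arms. It moves by x0.63 to x0.95 in the assumed examples with a pooled median and unequal follow-up.

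These sizes rest on assumed distributions, an assumed 7.5-year cap where stated, and rare events. The consequence is minor: one robustness check is hard to interpret, while the primary analysis and the power statement stand.

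**What to change.** Replace the fourth analysis with a re-estimation of the IRD and IRR in the claims-linked subset. Restrict it to patients whose enrollment covers the index date, use each patient's own enrollment end as the censoring date, and count events and person-time only up to that date. This extends the enrollment comparison already planned in the third analysis.

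If unlinked patients are to be included, multiply impute individual censoring times from the linked patients' distribution, given covariates, arm and calendar time of entry. No imputed time should end before an observed event or encounter. Section 9.2 already plans multiple imputation for covariates, so the machinery is familiar.

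If the median version is kept, state who receives it, whether it is pooled or arm-specific, whether it replaces or caps own time, and how endpoints and deaths on either side of it are handled.

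The cost is SAP wording and similar programming effort. The subset version uses fewer patients. How many fewer is unknown, because the 64% for NB counts linkage at any time and no linkage figure is given for lorcaserin initiators.

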**Figure 2. Case-crossover study design**

### 6.5.2 Outcomes and follow-up

The primary study endpoint is MACE, defined as the composite of:

- Medically attended non-fatal acute myocardial infarction;
- Medically attended non-fatal stroke;
- Cardiovascular-related death.

The secondary endpoints are:

- Individual components of MACE, analyzed separately, as (1) medically attended non-fatal acute myocardial infarction; (2) medically attended non-fatal stroke; and (3) cardiovascular-related death.

In accordance with the CAMELLIA-TIMI 61 trial, the comparability study will examine safety endpoints for the secondary objectives (2.0 and 2.1).

The safety endpoint was defined as a composite of:

- Cardiovascular death;
- Myocardial infarction;
- Stroke.

For all study objectives, information on myocardial infarction and stroke will be obtained from the EHR data, while information on death will be obtained from Datavant. Datavant compiles mortality data from government sources, obituaries, newspapers, and claims data for more than 90% of the U.S. population. Cause of death will be ascertained from the subset of individuals whose records can be linked to death certificates; otherwise, diagnoses adjacent to death will be identified, as feasible, using information from the EHR (e.g., cardiovascular-related hospitalizations or emergency department visits immediately preceding date of death).

A U.S.-licensed physician consultant, blinded to exposure, will review the detailed chronological listing of individual-level EHR data (and claims, where relevant) of a randomly selected subset of apparent MACE cases to determine whether MACE occurred. The adjudication process will compare the operational definition of MACE in the EHR to the physician's professional judgement and the occurrence of MACE in the EHR and claims data. If the initial EHR-based definition of MACE does not meet a pre-specified threshold for concordance, then adjustments to the initial list of diagnoses and procedure codes will be made to improve the accuracy of the operational definition of MACE.

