### 7.2 Datavant Death Data

We will link data from Arcadia to death data from Datavant, a private U.S. data curator, specializing in organizing health data. Datavant's mortality database contains information on deceased individuals in the U.S. and Canada. Datavant's Death Index contains information on individual deaths including year and month of death, gender, and cause of death, where available. Information is obtained from the Social Security Administration's Death Master File in addition to private obituaries, newspapers and claims data, and is updated on a weekly basis. In 2018, information was present for just over 2.4 million deaths.

In order to de-identify records, names, addresses, and social security numbers are removed in addition to modifications such as changing a person's date of birth to year of birth alone. Datavant's proprietary technology adds encrypted tokens to each record, constructed from the underlying personally identifiable information. Since these tokens correspond to unique individuals, they can be used to link death information to other health-related datasets.

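### One sensitivity censoring rule cuts follow-up short only for patients without a death record, and no specified analysis adds MI or stroke seen only in claims

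*Combined protocol and SAP*

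**What the plan says.** All of the following is in section 6.5.2 unless stated otherwise.

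- **General rule.** Patients are followed "until the first of the following censoring events": the endpoint, death, or "end of available data for those who do not have the event of interest (i.e., censoring due to end of available EHR data". The text does not say whether that last date is the patient's last encounter or the end of the database.
- **Alternative definitions.** Several are listed as robustness checks. One would "adjust the end of follow-up to be 6 months, 1 and 2 years following their last healthcare encounter in the EHR". Another would "compare follow-up times in the EHR to those observed in the claims enrollment files". The last takes the final visit to one of three provider types as the end, subject to a condition: "endocrinologist, or geriatric care provider in combination with no death information is the end of enrollment".
- **Event sources.** For every objective, "information on myocardial infarction and stroke will be obtained from the EHR data, while information on death will be obtained from Datavant". Section 7.2 describes the death index as holding "information on individual deaths including year and month of death, gender, and cause of death, where available".
- **Claims.** A blinded physician reviews EHR data, and claims where relevant, "of a randomly selected subset of apparent MACE cases to determine whether MACE occurred"; poor concordance leads to revised code lists. Section 6.5.1 uses claims to check whether prescriptions were filled. Section 6.2 says in general terms that linked claims will support sensitivity analyses. Section 10.1 concedes that encounters with non-contributing providers are not captured, but draws the consequence only for medication exposure.

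**The concern.** There are two gaps in the same section.

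First, under the last definition a survivor loses all person-time after the last selected visit. A patient with a death record does not meet the condition, stays under the general rule, and can be followed past that visit to death. Time at risk then depends on whether a death is recorded later. Deaths in the gap are counted while most of the person-time that produced them is dropped. The analysis is meant to test robustness, but its CV-death rates are biased upward, so a difference from the primary CV-death result would be hard to interpret.

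Second, an MI or stroke treated outside the contributing network is invisible to the outcome definition. The physician review starts from apparent cases, so it can find false positives but is not designed to find missed events. Equal under-capture in the two arms shrinks the incidence rate difference (IRD), which is the reassuring direction in a safety study. Unequal capture biases the rate ratio (IRR) as well, and no specified estimate would show it.

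**Working it through.** **The plan's own figure.** Section 8.2 claims more than 80% power for a relative risk of 2.0 at 2 per 1,000 person-years. With 37,000 versus 16,000 initiators and an assumed two-sided 5% test, power is 71% to 86% at a mean of 0.5 years of follow-up and 95% to 99% at 1 year, depending on the formula. The claim is plausible. The point here does not depend on it; I use only the rate of 2 and the relative risk of 2.0.

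**Assumptions.** The documents give no EHR loss rate, visit gap, CV-death share of MACE (f), share of late CV deaths that can be classified (p), or EHR capture (c). All are assumed below. Entry is taken as uniform to February 2020 (2020.17), from September 2014 (2014.7) for NB and from mid-2012 (2012.5) for lorcaserin; section 6.1 says only 2012. Mean windows T are (2020.17 − 2014.7)/2 = 2.735 years and (2020.17 − 2012.5)/2 = 3.835 years.

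**1. Gap only: nobody leaves the EHR, and all deaths in the gap are classified.** Survivors lose g years, so inflation of the CV-death rate = T/(T − g).

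| | g = 0.25 | g = 0.5 |
|---|---|---|
| Lorcaserin | 3.835/3.585 = 1.07 | 3.835/3.335 = 1.15 |
| NB | 2.735/2.485 = 1.10 | 2.735/2.235 = 1.22 |

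A separate model with random visits over a 3-year window gives 1.09 at 4 visits a year, 1.20 at 2, and 1.46 at 1. The size follows the gap.

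**2. Only if deaths after EHR exit are counted.** With loss rate λ, mean observed time D = mean of (1 − e^(−λT))/λ over entry dates, and inflation k = [D + p(T − D)]/D.
- NB, λ = 0.2, p = 0.25: D = 1.96; k = (1.96 + 0.25 × 0.775)/1.96 = 1.10.
- Lorcaserin, λ = 0.5, p = 0.5: D = 1.49; k = (1.49 + 0.5 × 2.345)/1.49 = 1.79.

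**3. Null MACE IRR.** IRR = [(1 − f) + f·k_NB]/[(1 − f) + f·k_lorc], with f = 0.1 to 0.3, p = 0.25 to 0.5, and k from step 2.

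| Annual loss | Entry windows as in 6.1 | Common entry window (NB's) |
|---|---|---|
| Equal, 20% to 50% | 0.94 to 1.00 | exactly 1.00 |
| NB 33%, lorcaserin 20% | 1.00 to 1.02 | 1.01 to 1.04 |
| NB 20%, lorcaserin 33% | 0.92 to 0.99 | 0.96 to 0.99 |

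The extremes, with p = 0.5 and f = 0.3: (0.7 + 0.3 × 1.198)/(0.7 + 0.3 × 1.494) = 0.92, and with a common window (0.7 + 0.3 × 1.340)/(0.7 + 0.3 × 1.198) = 1.04.

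**4. MI/stroke capture.** Rates of 4 and 2 per 1,000 person-years give a true IRD of 2.0. Observed IRD = 2.0 × [(1 − f)c + f].
- c = 0.8: 2.0 × (0.9 × 0.8 + 0.1) = 1.64, to 2.0 × (0.7 × 0.8 + 0.3) = 1.72.
- c = 0.5: 1.10 to 1.30.

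Equal capture leaves the IRR unchanged when the relative effect is the same across components. With 70% capture in NB and 80% in lorcaserin, a null IRR reads (0.9 × 0.7 + 0.1)/(0.9 × 0.8 + 0.1) = 0.89 at f = 0.1 and 0.92 at f = 0.3. Reversed, it reads 1.09 to 1.12.

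**The case against.** The definition at issue is one of several robustness checks, its estimates are to be compared with the others, and the MACE ratio hardly moves. That stands, and it limits the point to a sensitivity analysis.

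A reader might infer that the primary analysis also follows decedents past EHR exit while censoring survivors there. The documents do not support this. Stopping at the first of the listed events most naturally censors everyone at the end of EHR data. The third stop is worded for patients without the event and its date is undefined, so the handling of late Datavant deaths is unclear, but it is not shown to be wrong. For the same reason, the inflation of up to 1.79 in step 2 is conditional: if decedents also stop at EHR exit, only the gap effect remains.

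The ratio shift under equal loss comes entirely from unequal entry windows. Section 9.4 lists calendar time as a propensity-score covariate, though in the paragraph on the comparability cohort. If it also applies to the main cohort, lorcaserin starts before September 2014 would get little weight and much of that shift would go.

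The death condition may well be there for a reason: a visit precedes death, so a bare last-visit stop applied to everyone would count almost no deaths. That is why the condition cannot simply be deleted.

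On claims, it would be too strong to say that they play no part in outcome assessment. The physician review sees them, and section 6.2 leaves room for more. What remains true is that no effect estimate using claims-identified MI or stroke is specified.

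**Conclusion.** Both parts hold in limited form.

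The last censoring definition depends on a later outcome and inflates CV-death rates. The inflation is about 1.07- to 1.22-fold if follow-up otherwise ends at EHR exit, the gap is 3 to 6 months and all such deaths are classified. At that gap, it is larger only if deaths after EHR exit are counted. A null MACE IRR lies at about 0.92 to 1.04 under the assumed loss rates, and at 1.00 when loss and entry windows are equal. A reader might infer a material bias in the main MACE comparison; these figures do not show one.

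For MI and stroke, the plan specifies no estimate that adds claims-only events and none that shows whether EHR capture differs by arm. Equal under-capture at an assumed 80% reduces a true IRD of 2.0 to 1.64 to 1.72 per 1,000 person-years and spares the IRR; unequal capture biases both. The documents do not say whether capture is in fact low or unequal.

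The changes should be made, but nothing here invalidates the primary analysis.

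**What to change.** **(a) Censoring.** In the last definition, replace both the bare last-visit stop and the death condition with the last selected-provider encounter plus one fixed grace period, for example the 6 months, 1 and 2 years already used elsewhere in section 6.5.2. Apply it to every patient, whether or not they died. Count events, deaths and person-time only up to that date, and state how a death dated only to the month is placed relative to it. For the primary analysis, only clarify what the end of available EHR data means and that it applies equally to decedents and survivors.

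**(b) Claims outcomes.** Pre-specify a sensitivity analysis of objective 1.0 in the claims-linked subset, with MI and stroke from EHR or claims and follow-up bounded by claims enrolment for everyone. Report EHR capture of claims-identified MI and stroke by arm.

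**Cost.** This needs SAP wording and one added analysis; the enrolment files are already to be used. Fewer deaths are counted under (a), and for patients who left the EHR no MI or stroke can be seen during the grace period.

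The linked subset is smaller. NB: 0.64 × 37,000 = 23,680. The lorcaserin share is not given; 46% (the figure for all EHR patients in section 7.1) to 64% of 16,000 gives 7,360 to 10,240. At 2 per 1,000 person-years and an assumed 2 years of follow-up, expected events are 148 and 64 in full, and 94.7 and 29.4 to 41.0 when linked. The 95% CI factor for the IRR, exp[1.96√(1/e_NB + 1/e_lorc)], widens from 1.34 to 1.44 to 1.51. If matching weights act like 1:1 matching, exp[1.96√(2/e_lorc)] goes from 1.41 to 1.54 to 1.67. Either can still exclude a doubling when the true IRR is 1.
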